## **8.2. Efficacy Assessments**

### **8.2.1. Standardized Standing Test**

Efficacy will be assessed using a standardized standing test. The standardized standing test mimics daily activities of POTS in a standardized manner [Finucane et al, 2019], and is therefore considered to be an objective, interpretable, and meaningful measurement to both patients and health care professionals.

In general, subjects are asked to lie supine for 10 minutes to achieve stable baseline blood pressure (BP) values. At the end of the 10 minutes, baseline HR and BP will be assessed. After rest, subjects are asked to stand up as quickly as possible during inspiration (where possible) to minimize straining and arm movement. Heart rate and BP will be assessed at 1, 3, 5, 7 and 10 minutes after standing. Subjects are then asked to sit or lie down until they have recovered. A separate standardized standing test protocol will be provided to sites with more detail on how to perform this assessment.

The standardized standing test will be performed as the last assessment at the time points specified in the Schedule of Activities (Section 1.3).

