#### 9.4.2.1. Primary Estimand and Analysis of Primary Efficacy Endpoint

The subject's response status of no longer meeting diagnostic criteria of post-COVID POTS as measured by standardized standing test (ie, no longer experiencing HR increase of  $\geq 30$  bpm, in the absence of 20 mmHg decrease of HR [orthostatic hypotension]) will be assessed as the primary endpoint.

A subject is considered a responder if

$$\begin{aligned} \text{HR}_{\text{W25,10min}} - \text{HR}_{\text{W25,0min}} &< 30 \text{ bpm} \quad \text{and} \\ \text{BP}_{\text{W25,as}} - \text{BP}_{\text{W25,bs}} &> -20 \text{ mmHg} \end{aligned}$$

Where,  $\text{HR}_{\text{W25,10min}}$  indicates the average of the 2 highest HR measures (bpm) within 10 minutes after start of the standing test at W25,  $\text{HR}_{\text{W25,0min}}$  indicates the HR measure (bpm) at start of the standing test at W25,  $\text{BP}_{\text{W25,as}}$  indicates the systolic blood pressure measure (mmHg) at any time point within 10 minutes after start of the standing test at W25, and  $\text{BP}_{\text{W25,bs}}$  indicates the systolic blood pressure measure at the start of the standing test at W25.

Consequently, a subject is considered a non-responder, if

$$\begin{aligned} \text{HR}_{\text{W25,10min}} - \text{HR}_{\text{W25,0min}} &\geq 30 \text{ bpm} \quad \text{or} \\ \text{BP}_{\text{W25,as}} - \text{BP}_{\text{W25,bs}} &\leq -20 \text{ mmHg} \end{aligned}$$

Response rates [%] will be determined for placebo and IgPro20.

For each treatment group point estimates and 95% Wilson Score confidence intervals will be provided, for the difference between treatment groups (IgPro20 – placebo) the point estimate, 95% Farrington-Manning confidence interval and 1-sided p-value will be provided.

To show the magnitude of the HR increase at baseline ( $HR_{10min, baseline} - HR_{0min, baseline}$ ) and at W25 ( $HR_{10min, W25} - HR_{0min, W25}$ ), the proportion of subjects within the following categories will be analyzed. This analysis will show the proportion of the subjects with normal HR increase after the standing test at the end of the treatment period.

- HR increase < 10 bpm
- $10 \text{ bpm} \geq \text{HR increase} < 15 \text{ bpm}$
- $15 \text{ bpm} \geq \text{HR increase} < 20 \text{ bpm}$
- $20 \text{ bpm} \geq \text{HR increase} < 25 \text{ bpm}$
- $25 \text{ bpm} \geq \text{HR increase} < 30 \text{ bpm}$
- $30 \text{ bpm} \geq \text{HR increase} < 35 \text{ bpm}$

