8.2.2. Heart Rate and Change in Heart Rate During Standardized Standing Test

Heart rate for standing test will be measured at the end of the 10 minutes in supine position and at 1, 3, 5, 7, and 10 minutes of standing.

The change in heart rate during the standing test is calculated as the difference of the average of the two highest heart rate measures (bpm) within 10 minutes of standing and the heart rate measure (bpm) at the end of the 10 minutes in supine position.

If in one subject the standardized standing test was repeated at a visit results of the last standing test will be used for the summarizing analysis.

8.2.3. Systolic Blood Pressure and Change in Systolic Blood Pressure During Standardized Standing Test

Blood pressure for standing test will be measured at the end of the 10 minutes in supine position and at 1, 3, 5, 7, and 10 minutes of standing.

The change in systolic blood pressure during the standing test is calculated as the difference of the minimum of all systolic blood pressures (mmHg) within 10 minutes of standing and the systolic blood pressures (mmHg) at the end of the 10 minutes in supine position.

If in one subject the standardized standing test was repeated at a visit results of the last standing test will be used for the summarizing analysis.

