10.1. Standardized Standing Test

Efficacy will be assessed using a standardized standing test. The standardized standing test mimics daily activities of POTS in a standardized manner [Finucane et al, 2019], and is therefore considered to be an objective, interpretable, and meaningful measurement to both patients and health care professionals.

In general, subjects are asked to lie supine for 10 minutes to achieve stable baseline blood pressure (BP) values. At the end of the 10 minutes, baseline HR and BP will be assessed. After rest, subjects are asked to stand up as quickly as possible during inspiration (where possible) to minimize straining and arm movement. Heart rate and BP will be assessed at 1, 3, 5, 7 and 10 minutes of standing. Subjects are then asked to sit or lie down until they have recovered. A separate standardized standing test protocol will be provided to sites with more detail on how to perform this assessment.

The standardized standing test will be performed as the last assessment at the time points specified in the Schedule of Activities.

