10.2.2. Analysis of Primary Endpoint

The subject's response status of no longer meeting diagnostic criteria of post-COVID POTS as measured by standardized standing test (ie, no longer experiencing HR increase of ≥ 30 bpm, in the absence of 20 mmHg decrease of SBP [orthostatic hypotension]) will be assessed as the primary endpoint.

A subject is considered a responder if,

$$\begin{aligned} \text{HR}_{W25,10\text{min}} - \text{HR}_{W25,0\text{min}} &< 30 \text{ bpm} \text{ and} \\ \text{SBP}_{W25,\text{as}} - \text{SBP}_{W25,\text{bs}} &> -20 \text{ mmHg} \end{aligned}$$

Where, $\text{HR}_{W25,10\text{min}}$ indicates the average of the two highest HR measures (bpm) within 10 minutes after start of the standing test at W25, $\text{HR}_{W25,0\text{min}}$ indicates the heart rate measure (bpm) at start of the standing test at W25, $\text{SBP}_{W25,\text{as}}$ indicates the systolic blood pressure measure (mmHg) at any time point within 10 minutes after start of the standing test at W25, and $\text{SBP}_{W25,\text{bs}}$ indicates the systolic blood pressure measure at the start of the standing test at W25.

consequently, a subject is considered a non-responder if,

$$\begin{aligned} \text{HR}_{W25,10\text{min}} - \text{HR}_{W25,0\text{min}} &\geq 30 \text{ bpm} \text{ or} \\ \text{SBP}_{W25,\text{as}} - \text{SBP}_{W25,\text{bs}} &\leq -20 \text{ mmHg} \end{aligned}$$

Response rates [%] will be determined for placebo and IgPro20.

Due to the premature termination of the study not all randomized subjects completed the Double-blind Treatment Period, thus the assessment of response at Week 25 is not always possible. For that reason, response will be assessed by visit based on the available data at each of the following visits, ie., Week 5, Week 9, Week 13, Week 17, Week 21 and Week 25. The multiple imputation strategies as planned in the study protocol for handling missing data will not be performed (see Section 5). For the following intercurrent events, the composite strategy will be applied, and the subject will be considered non-responder for all visits following the ICE:

Table 10: Definition of response for specific ICEs

Intercurrent Event	Strategy	Description	Imputation details for response
Treatment (IMP) discontinuation due to LoE, related adverse event or lack of compliance	Composite	Discontinuation due to lack of efficacy, related adverse event or lack of compliance will be treated as a failure.	For all visits following ICE: non-responder

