Prohibited therapies	Composite	Data after the intake of prohibited medication with a potential effect on the primary endpoint will be treated as failure.	For all visits following ICE: non-responder
Death related to IMP or disease	Composite	Death will be considered as treatment failure.	For all visits following ICE: non-responder

CONFIDENTIAL

All symptoms that have been collected during the standardized standing test will be listed.

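### The responder rule sets no minimum number of standing readings, so a standing test stopped early is more likely to score as a response than the same test completed

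*SAP*

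**What the plan says.** Protocol 8.2.1 sets the measurement times: after 10 minutes supine, "Heart rate and BP will be assessed at 1, 3, 5, 7 and 10 minutes after standing". SAP 10.1 repeats them.

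Protocol 9.4.2.1 and SAP 10.2.2 define response at Week 25 by two conditions. The HR increase must be below 30 bpm, where the standing value "indicates the average of the two highest HR measures (bpm) within 10 minutes after start of the standing test at W25" (SAP wording; the protocol's is the same in substance). In addition, SBP must not fall by 20 mmHg or more.

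SAP 8.2.2 derives the HR change from "the average of the two highest heart rate measures (bpm) within 10 minutes of standing" minus the supine reading. SAP 8.2.3 derives the SBP change from the "minimum of all systolic blood pressures (mmHg) within 10 minutes of standing" minus the supine reading.

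None of these sections states a minimum number of readings or a rule for a test that ends early. The only rule at test level (SAP 8.2.2 and 8.2.3) is that the last test counts when a test was repeated. Early stopping is not an intercurrent event in protocol Table 5 or SAP Table 10. SAP 10.2.2 assesses response at Weeks 5, 9, 13, 17, 21 and 25 on whatever data are available, without multiple imputation. Symptoms do not enter the response definition: "All symptoms that have been collected during the standardized standing test will be listed".

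**The concern.** Response is meant to show that the subject no longer meets the POTS criterion, which is an HR rise of at least 30 bpm within 10 minutes of standing. A positive result can be established early. A negative one cannot be established from the first minutes alone. The scoring rule treats the two alike.

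Take a subject who sits down after the 3-minute reading with increases of 24 and 27 bpm and no SBP fall. The average is (24 + 27)/2 = 25.5 bpm, and the rule scores a response. One later reading of 33 bpm or more would have reversed this, because (27 + 33)/2 = 30.

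The primary endpoint, the by-visit response rates and the HR-increase key secondary endpoint all use this value. A misclassified subject therefore appears in more than one result.

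**Working it through.** **Plan's own figure.** Inputs from SAP 4.5: 30% and 60% response, 2:1 allocation, one-sided alpha 2.5%, 90% power. With a null difference of zero, the Farrington-Manning test uses the pooled proportion, (0.30 + 2 × 0.60)/3 = 0.50. Placebo n = [1.960 × √(1.5 × 0.25) + 1.282 × √(0.21 + 0.24/2)]² / 0.30² = 41.7, so 42 placebo and 84 active. The total of 126 reproduces, with power 0.902. The point concerns the scoring rule, not this figure.

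**Direction (no assumptions).** Let k be the number of standing readings obtained, k ≥ 2.
- The mean of the two largest of the first k values cannot exceed the mean of the two largest of all five.
- The minimum of the first k SBP values cannot be lower than the minimum of all five.
- Both response conditions are therefore at least as easy to meet with k readings as with five.
- With k = 1 there is no average of two, and the HR value cannot be computed.

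**Size, HR part.** The within-test SD and the shape of the HR profile are assumptions; the documents give neither. With no time trend, the mean of the two highest lies 0.83 SD above the true level with 5 readings, 0.42 SD with 3 and 0 SD with 2. So a two-reading value is low relative to the full-test statistic, not relative to the true level: 0.83 × 4 = 3.3 bpm to 0.83 × 6 = 5.0 bpm.

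For a flat rise of 33 bpm and two readings, the average has SD σ/√2, so P(<30) = Φ(−3√2/σ):
- σ = 4: Φ(−1.06) = 0.144
- σ = 6: Φ(−0.71) = 0.240

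Simulation with five readings gives 0.001 and 0.006.

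Simulated P(HR part met) for other assumed profiles, SD 4. The 1-minute reading is at 75% of the plateau for a slow rise and 55% for a steep rise:

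| Plateau | Profile | 5 readings | 3 readings | 2 readings |
|---|---|---|---|---|
| 35 bpm | flat | 0.000 | 0.003 | 0.039 |
| 35 bpm | slow rise | 0.005 | 0.276 | 0.761 |
| 35 bpm | steep rise | 0.045 | 0.877 | 0.998 |
| 45 bpm | flat | 0.000 | 0.000 | 0.000 |
| 45 bpm | slow rise | 0.000 | 0.000 | 0.017 |
| 45 bpm | steep rise | 0.000 | 0.052 | 0.746 |

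For comparison, a subject with a 25 bpm plateau and a full test meets the HR part with probability 0.78 (flat) to 0.98 (steep).

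**Size, SBP part.** With an assumed mean change of −10 mmHg and SD 7, the SBP condition is met with probability 0.673 on five readings and 0.854 on two.

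**Effect on the design as planned.** Suppose a share s of true non-responders in both arms stops early and a fraction f of these is scored as response. Then placebo = 0.30 + 0.70sf and active = 0.60 + 0.40sf.
- s = 10%, f = 50%: 33.5% v 62.0%, power 0.867 at 126.
- s = 20%, f = 50%: 37.0% v 64.0%, power 0.827 at 126 and 0.932 at 177.

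Both s and f are assumptions.

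**Effect on the analysis now planned.** Sixteen subjects at 2:1 is about 11 and 5. One misclassified subject moves an arm's rate by 1/11 = 9 points or 1/5 = 20 points, if all are assessed at that visit.

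**The case against.** The strongest reply is that the documents do not say a stopped test is scored on the readings obtained. That follows only from applying the formula to a case the text does not mention. Treating such a test as missing is also open. Two documents not available here could hold a rule: the separate standing test protocol for sites (protocol 8.2.1, SAP 10.1) and the analysis dataset specifications, which SAP 8.2 says give full derivation details.

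This stands as a caution about what will actually be done. It does not repair the SAP. Two or three readings give a computable value, SAP 10.2.2 works from available data, and nothing sets that value to missing. If it were set to missing, the subject would leave the denominator, and that choice should be stated too.

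A reader might infer that the most symptomatic subjects are the most likely to be counted as responders. The documents do not support this. A large early HR rise remains a non-response on two readings, a subject who stops after one reading has no computable HR value, and a mild subject with a full test usually has the higher chance of response. Nor does the entry threshold of 40 on COMPASS-31 select for orthostatic intolerance. It is a total over six domains, and under SAP Table 5 the orthostatic domain supplies at most 40 of the 100 points, so 40 can be reached without it. Exclusion criterion 20 also removes subjects with a contraindication to the standing test.

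It is also fair to object that counting intolerance as non-response adds a tolerance component to an endpoint defined by HR and SBP. The fix therefore includes a display without it.

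**Conclusion.** The point holds in a limited form. The rule has no completeness condition, and for any test with at least two readings, stopping early can change the score only towards response. That direction needs no assumption. The size does: in the examples above it runs from negligible (flat profile, plateau 45 bpm) to near-certain misclassification (steep profile, plateau 35 bpm, two readings).

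The documents do not show how often tests stop early or in which arm. More stops on placebo would shrink the treatment difference; more on IgPro20 would inflate it. A reader might infer a known bias in the comparison, but the documents support no direction between arms.

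SAP version 2.0 makes no test and states that the primary estimand cannot be assessed, so no error rate or decision is affected. What remains at risk is the reading of small by-visit response rates, for which SAP 10.2.3 plans no sensitivity analysis. Severity is moderate; it is not a must-fix.

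**What to change.** In SAP 8.2.2, 8.2.3 and 10.2.2, add one derivation rule:
- A subject is a responder at a visit only if the 10-minute reading was obtained.
- An incomplete test that already shows an HR increase of 30 bpm or more, as derived in SAP 8.2.2 (so from at least two readings), or an SBP fall of 20 mmHg or more, is non-response.
- Any other incomplete test is non-response if stopped for orthostatic symptoms, judged from the symptoms collected during the test, and missing if stopped for technical reasons.
- Add a display that treats all tests in this last group as missing.

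List the number of readings per test by arm and visit, and summarise the HR-increase endpoint with and without incomplete tests. Protocol 9.4.2.1 has the same gap, which matters if the definition is reused.

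The cost is SAP wording, one line of derivation, a listing and a few extra summaries. Response rates may fall slightly. Neither document confirms that the reason for stopping is recorded, so it may have to be inferred from the listed symptoms.

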10.2.3. Sensitivity and Supplementary Analyses of Primary Endpoint

Not applicable.

10.2.4. Subgroup Analyses of Primary Endpoint

Not applicable.

10.3. Key Secondary Estimand

According to the study protocol, the key secondary interest was to quantify the treatment effect of IgPro20 under the hypothetical situation where no subjects withdraw from treatment or the study before Week 25 with the key secondary estimand details provided in CSP Section 9.4.2.1.1. Due to the premature termination of the study not all randomized subjects completed the double-blind period, thus the assessment of the key secondary endpoints at Week 25 is not always possible. For that reason the key secondary endpoints as defined in Section 10.3.1 will be assessed based on the available data at each of the following visits: Week 5, Week 9, Week 13, Week 17, Week 21 and Week 25 and for each treatment group the respective descriptive statistics will be provided by visit. The multiple imputation strategies as planned in the study protocol for handling missing data will not be performed (see Section 5).

10.3.1. Analysis of Key Secondary Endpoints

The following key secondary efficacy endpoints are defined:

1. Change from baseline in OI score of COMPASS-31 at the end of the Double-blind Treatment Period

For each subject $OI_{\text{change}} = OI_{W25} - OI_{\text{baseline}}$ will be calculated, where OI_{W25} corresponds to the OI score of COMPASS-31 at Week 25 and baseline, respectively. Descriptive statistics of the individual changes will be calculated by treatment group.

2. Change from baseline in TS score of COMPASS-31 at the end of the Double-blind Treatment Period:

For each subject $TS_{\text{change}} = TS_{W25} - TS_{\text{baseline}}$ will be calculated, where $TS_{W25} / TS_{\text{baseline}}$ correspond to the TS score of COMPASS-31 at Week 25 and baseline, respectively. Descriptive statistics of the individual changes will be calculated by treatment group.

3. Change from baseline in HR increase within 10 minutes of standing test at the end of the Double-blind Treatment Period:

For each subject $HR_{\text{change}} = (HR_{W25,10\text{min}} - HR_{W25,0\text{min}}) - (HR_{\text{baseline},10\text{min}} - HR_{\text{baseline},0\text{min}})$ will be calculated, where $HR_{W25,10\text{min}}$ indicates the average of the two highest HR measures (bpm) within 10 minutes after start of the standing test at W25, $HR_{W25,0\text{min}}$ indicates the HR measure (bpm) at start of the standing test at Week 25, and likewise for baseline. Descriptive statistics of the individual changes will be calculated by treatment group.

10.3.2. Sensitivity Analyses of Key Secondary Endpoints

Not applicable.

10.3.3. Subgroup Analyses of Key Secondary Endpoints

Not applicable.

10.4. Analysis of Secondary Efficacy Endpoint

Not applicable.

10.5. Multiplicity

Not applicable.

10.6. Multiple Imputation

The originally planned multiple imputation process will not be done due to the low sample size and the sparseness of the data (see Section 5).

10.7. Tipping Point Analysis

Not applicable.

10.8. Analysis of Exploratory Endpoints

The following exploratory endpoints will be summarized descriptively similarly to secondary efficacy endpoints. No comparison between treatment sequences will be done.

10.8.1. Analysis of Patient Reported Outcomes

Analysis of additional PROs will be restricted to the Malmö Symptom score and the OHQ score. The responses to each question will be summarized by assessment point and treatment group. The absolute mean changes from baseline in all total (if available) and domain (if available) scores assessments will be summarized. The following scores will be summarized for each assessment time:

- Change in Malmö Symptom score.

CONFIDENTIAL

- Change from baseline in the 2 domains of the OHQ score and in the OHQ composite score.
- Responses to PGI-S and PGI-C for OI symptoms.

10.8.2. PK parameters

Not applicable.

11. SAFETY ANALYSES

All Safety analyses will be performed for the following period and analysis set:

- Double-blind treatment period: Week 1 – Week 25 by treatment groups (SAF)

11.1. Extent of Exposure

Exposure to the IMP will be descriptively summarized by treatment groups:

- Duration of exposure (days) per subject.
- Number of infusions (partial or complete) administered per subject.
- Number of days with infusions per subject.
- Total dose received (g) per subject.
- Total volume received (mL) per subject.

Extent of exposure will also be described for subjects treated with IgPro20 in any treatment period.

The listing of individual subject data will include all variables presented in the summary tables.

11.2. Adverse Events

Adverse events will be coded using the Medical Dictionary for Regulatory Activities (MedDRA) version 26.1 or higher. TEAEs are defined as AEs started after the start of the first infusion of IMP. All AEs regardless of when they were reported will be listed.

An AE will be counted in the respective analysis if the onset of the event falls within the period. For the definition of start and end of the periods see [Table 9](#).

- An overview summary of TEAEs, including number of subjects, percentages of subjects, the number of events, including the following:
 - Any TEAE.
 - TEAEs related to IMP.
 - Temporally associated TEAEs (defined as an AE with an onset between the start of the IMP infusion and up to 72 hours after the end of IMP infusion).

- TEAEs leading to permanent discontinuation of IMP.
- TEAEs leading to withdrawal from study.
- TEAEs leading to IMP dose interruptions.
- Serious TEAEs.
- Serious TEAEs related to the IMP.
- Temporally associated serious TEAEs.
- Fatal serious TEAEs.

The following descriptive tables will be generated for TEAEs, including number of subjects, percentages of subjects, and the number of events:

- TEAEs by System Organ Class (SOC) and Preferred Term (PT).
- TEAEs by SOC, PT, and maximum severity (presenting number and percentages of subjects).
- Causally related TEAEs by SOC and PT.
- Temporally associated TEAEs by SOC and PT.
- All AE summaries presented by SOC and preferred term will include a virtual SOC comprising of local reactions, ie, all AEs reported within the MedDRA High level terms “Administration site reactions NEC” or “Infusion site reactions” or “Injection site reactions”. Local reactions will be analyzed by using a virtual SOC called “local adverse events”.

All tables will be displayed in descending order of total incidence by preferred term and by SOC and PT, respectively.

Number of events are counted within the respective period and treatment group.

Temporally associated TEAEs are defined as AEs with an onset between the start of the infusion and up to 72 h after the end of IMP infusion. In case time of onset of AE is missing, the AE is considered temporally related, if the onset of the AE is between the day of the start of infusion and the day of the end of infusion + 3 days (inclusive).

The following listings will be provided:

- All Adverse Events
- All serious TEAEs

